# **1. Administration information**

## **Title and trial registration**

A randomized controlled trial to examine the efficacy of vaporised nicotine products and telephone quit line support compared with nicotine replacement therapy and telephone quit line support when used following discharge from residential withdrawal services

## **Trial registration**

ANZ Clinical Trial Registration Number: [ACTRN12619001787178]

## **Protocol Version**

Version 6, Dated 10-03-2021

## **2. Introduction**

### **2.1. Background and rationale**

Up to 95% of people in AOD treatment smoke tobacco. People with substance use disorders experience great difficulty quitting tobacco smoking. As a result, quit rates are close to zero, and tobacco-related diseases are the leading cause of mortality. New ways for addressing smoking in this population are needed. Vaporised nicotine products (VNPs) hold significant potential as both cessation aids and harm reduction support. There is now good evidence of safety, and emerging evidence that VNPs assist cessation. More evidence of the safety and effectiveness of VNPs for populations with high smoking prevalence rates and low quit rates is desperately needed. Many AOD withdrawal facilities are smoke-free, and service users achieve brief abstinence. However, most return to smoking immediately following discharge, representing a missed opportunity for supporting long-term abstinence. Providing smoking cessation support post discharge will assist individuals with moderate to heavy nicotine dependence to remain smoke-free in the community. The aim of this world-first trial is to test the effectiveness of VNPs at increasing smoking cessation amongst AOD residential withdrawal services. Service users (n=926) from six residential and inpatient withdrawal AOD services across three states (NSW, Victoria, and Queensland) will be recruited and randomised. Participants in the comparison condition will receive current best-practice combination nicotine replacement therapy (NRT). Participants in both groups will also receive proactive Quitline support from AOD-trained counsellors. The trial will build on our pilot study in a Victorian AOD withdrawal facility which found the design and the interventions highly feasible and acceptable to both service users and staff.

### **2.2. Objectives**

The purpose of this trial is to test the effectiveness of VNPs and Quitline (telephone counselling) compared to current best practice combination NRT and Quitline at increasing smoking cessation among clients following discharge from an inpatient drug and alcohol withdrawal service.

#### **2.2.1. Primary Objective**

The primary objective is to examine, using a randomised controlled trial, the effectiveness of VNPs on self-reported 7-month continuous abstinence (from tobacco smoking) at 9-months follow-up.

#### **2.2.2. Secondary objectives**

Additional secondary objectives are to compare participants in the VNP + Quitline to those in the NRT + Quitline group on:

- i) Biochemically verified 7-month continuous abstinence at month 9
- ii) 30-day point prevalence abstinence at months 3 and 9
- iii) Reduction in cigarettes smoked per day at months 3 and 9
- iv) Reduction in strength and urges to smoke tobacco at months 3 and 9
- v) Reduction in withdrawal symptoms at months 3 and 9
- vi) Relapse episodes to smoking at months 3 and 9

Other objectives involve:

- i) Assessing treatment adherence (duration/ use of products/ reasons for non-use/ engagement with telephone counselling) compared by treatment group
- ii) Assess attitudes/ acceptability of the provided interventions
- iii) Use of additional pharmacotherapies, visits to GPs, and use of print and online materials
- iv) Assess provided interventions on mood

## 3. Study Methods

### 3.1. Trial Design

Project NEAT is a two-arm, single blinded, parallel group randomised (1:1) trial with a 6-month post intervention follow-up (or 9-months post discharge). The trial has been designed to conform to the CONSORT statement.

### 3.2. Intervention Groups

#### 3.2.1. Group 1: VNP + Quitline

- An information pack that includes printed information on benefits of quitting (including benefits on AOD reduction); information about nicotine maintenance and elaboration of the benefits of vaping instead of smoking and the risks of vaping compared to complete abstinence. The lack of data on health risks of long-term vaping will be highlighted. Instructions on how to use VNPs and safe storage and handling will be included.
- Provision of two VNP kits + 12 weeks of liquid nicotine along with 1-week supply of NRT patches. The device (Innokin Endura T18-II starter kit) and refill liquid (Nicophar) were selected based on quality assurance and compliance with relevant standards (GMP (good manufacturing practice) for liquid). Participants will be provided with two VNPs and an initial 4-week supply of liquid nicotine, with further supplies of the refill liquid mailed or couriered to them at 4 weekly intervals. Participants will be advised to use both the NRT patches (1 week supplied) and the VNP for the first week following discharge while they are learning how to use the VNP effectively.
- *Medicine: liquid nicotine (or e-liquid)*. The liquid nicotine will be manufactured to GMP standards for the trial (Nicophar brand). It will be provided to participants in 10ml dropper bottles. Each 12mg strength 10mL bottle will contain nicotine (1.2%), Glycerol (84%) and water (14.8%).
- Proactive referral to Quitline counselling (call-back service) which provides calls at pre-discharge and on days 1, 3, 7, 14 & 28 post-discharge, with an emphasis on relapse prevention. At least one call will additionally be conducted during stay at AOD treatment facility. The total number and timing of calls will be tailored to client need and smoking status, i.e. more frequent calls around relapse crises/quit attempts with an approximate 10 calls over 12 weeks. Participants will be text messaged prior to being called as AOD clients are unlikely to pick up calls from a private number. Counsellors will be provided with training around the use of VNP, monitoring and

encouraging correct use of NRT and working with clients to address barriers to their use.

### **3.2.2. Group 2: NRT + Quitline**

- Participants randomised to group 2: standardised smoking care will receive the following:
- An information pack that includes printed information on benefits of quitting (including benefits on AOD reduction), and instructions on how to use NRT correctly, for how long, potential side effects (and when to notify a health care provider), safe storage and handling.
- Provision of 12 weeks of nicotine replacement therapy – transdermal (e.g. patches) and oromucosal forms (e.g. gum, lozenge, mouth spray) of NRT to be used throughout the intervention period. For weeks 1–4 participants will receive: 4 x QuitX 21mg Patches 7s, 2 x Nicorette Inhalator 15mg 20s, and 3 x Nicorette Quick Mist 1mg spray. For weeks 5-8 participants will receive: 4 x QuitX 21mg Patches 7s, 2 x Nicorette Inhalator 15mg 20s, 1 x Nicorette Cool Drops 4mg 80s, and 1 x quitX Gum 4mg 100s Mint. For weeks 9–12 participants will receive 1 x Nicabate 21mg Patches 28s, 2 x Nicorette Inhalator 15mg 20, 2 x Nicorette Cool Drops 4mg 80s. This will be mailed to an address the participant supplies.
- Proactive referral to Quitline counselling (call-back service) which provides calls on days 1, 3, 7, 14 & 28 post-discharge, with an emphasis on relapse prevention. At least one call will additionally be conducted during the stay at the AOD treatment facility pre-discharge. The total number and timing of calls will be tailored to client need and smoking status, i.e. more frequent calls around relapse crises/quit attempts with an approximate 10 calls over 12 weeks. Participants will be text messaged to alert them to expect a Quitline call prior to being called as AOD clients are unlikely to pick up calls from a private number. Counsellors will monitor and encourage correct use of NRT and work with clients to address barriers to its use.

## **3.3. Randomisation**

The randomisation component of the study is embedded into a REDCap project database. Participating site research assistants/ coordinators will access the randomisation module following the completion of the baseline survey with participants via the web enabled iPad. An independent statistician supervised by CI [name] from the Statistical Support Unit at Hunter Medical Research Institute (HMRI) produced the randomisation schedule using a permuted block randomisation procedure, with random blocks of size 4 or 6), stratified by site, and equal allocation ratios for the two treatment arms. This was coded using the SAS programming language and uploaded to the REDCap database.

## **3.4. Sample Size**

Studies using continuous abstinence measures with mental illness and AOD samples have found smoking cessation rates close to zero at longer term follow-up using NRT. Thus, for this trial, with our sample of heavy smokers with concurrent AOD use, we will conservatively assume a verified continuous abstinence rate of 3% at 6 months follow up in the NRT +Quitline usual care control group.

A sample of 278 smokers in each treatment group are needed to detect a difference of 6% between groups (i.e., 3% in NRT group and 9% in VNP group continuous abstinence at 9-month follow-up) using a two-tailed test with 80% power and a 5% type 1 error rate. Our pilot study at the Wellington House withdrawal unit in Melbourne recruited approximately two participants per week. Assuming similar recruitment rates and 40% attrition rate at 9 months follow-up (based on TNT trial GNT1045840), we will require a sample size of 926 eligible smokers across the 6 sites. We are allowing two years for participant recruitment to achieve this, based on our pilot study.

### **3.5. Hypothesis**

The primary null hypothesis: Compared to those allocated to current best-practice NRT +Quitline (control group), participants receiving the VNPs +Quitline (intervention group) will have an equal proportion of participants with self-reported 7-month continuous abstinence at 9-months follow-up.

### **3.6. Screening data**

Staff members at the service will notify AOD clients that their service is currently participating in a research study to help people quit tobacco smoking. Staff members at participating services will briefly ask whether the individual identified as a current tobacco smoker on entering the service. The staff member will provide a copy of the participant information statement and will ask the AOD client if they would like the study research assistant to discuss the project further with them. If the AOD client reports no, then the AOD staff member will thank them for their time. If the AOD client reports yes then the staff member will notify the study research assistant (who may be a trained current employee of the participating AOD site or a trained research assistant/trial coordinator).

The research assistant will ask if this is a good time to discuss the project. If not the research assistant will make time the following day or so to discuss. The research assistant will approach the client and then commence the screening and enrolment log on REDCap.

### **3.7. Eligibility**

#### **3.7.1. Inclusion Criteria**

- Aged 18 or over
- Daily tobacco smoker (10 or more cigarettes) on entering withdrawal unit
- Accessing treatment from participating services
- Receiving NRT while in treatment at participating services
- Want to quit smoking in the next 30 days
- Has capacity to consent and able to understand the participant materials and follow the study instructions and procedure (e.g., sufficient English language ability and not too unwell as judged by medical staff)

#### **3.7.2. Exclusion Criteria**

- Pregnant or breastfeeding (measured by self-report)
- Enrolled in another study

- Scheduled to be transferred to a long-term residential rehabilitation service following discharge from the withdrawal unit
- Used VNP (containing nicotine) in the last 30 days
- Currently engaged in Quitline’s call-back services
- Prescribed stop smoking medication (e.g., varenicline or bupropion)
- No ready access to a phone

### 3.8. Recruitment

The primary mode of recruitment will be via RAs at participating services. Staff at participating services will be asked to notify potential participants about the study and to ask if they would like to speak to the RA about the study. For every client that speaks to the RA, the RA will record this in the screening and enrolment log (via iPad on REDCap). Additional recruitment strategies will be via flyers provided to participants on entry to the service, or in their pre-entry pack to the participating service, as well as flyers in the communal areas of the service to encourage self-referral.

### 3.9. External Data Sources

The sole external data source is Quitline Victoria who will be collecting the following information:

- Length of call
- Number of calls
- Session content

## 4. ANALYSIS

### 4.1. Outcome Definitions

#### 4.1.1. Primary outcome

Self-reported 7-month continuous abstinence (dichotomous: abstinent or not) at 9 months post randomization

Self-reported 7-month continuous abstinence will be assessed using the following items:

- “Do you currently smoke any tobacco products?” (response options: yes daily; yes, at least once a week; yes, less often than once a week; **no, not at all**)
- “How long ago did you last smoke every day?” (response options: Less than 1 week; 1 week to 1 month; 1 – 3 months; 4 – 6 months; **7 – 9 months; more than 9 months**) reporting either “7-9 months”, “or more than 9-months”.

Participants that report they are currently ‘not smoking at all’ AND that it has been either ‘7-9 months’ or ‘more than 9 months’ since they last smoked every day are considered to have reached 7-months continuous abstinence.

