#### 4.1.2. Secondary outcomes

i) Biochemically verified 7-month continuous abstinence from tobacco smoking (dichotomous: abstinent or not)

- Self-reported 7-month continuous abstinence at 9-month survey will be verified using measures of CO in expired air. A cut-off point of 8ppm will be used to define a smoker (i.e. CO level <8ppm will be considered biochemically verified abstinent).

ii) 30-day point prevalence abstinence (PPA)

- Two items will be used to assess self-reported 30-day PPA: "Have you smoked at all, even a puff, in the last 30 days?" (response options: yes; **no**), and "How many cigarettes have you smoked in the last 30 days?" (response options: **less than 1 or just a puff**; 1 – 5; 6 – 10; 11 – 20; more than 20).

Participants who report not having smoked in the last 30 days AND smoking 'less than 1' cigarette or 'just a puff' in last 30-days will meet 30-day PPA criteria.

iii) 7-day PPA

- Self-reported 7-day PPA will be measured by asking participants "Have you smoked at all, even a puff, in the last 7 days?" with response options a) yes, b) no. Responding 'no' will equate to self-reported 7-day PPA.

iv) Number of cigarettes smoked and percentage reduction from baseline (dichotomised: at least 50% or < 50%)

- Participants will be asked "currently how many cigarettes do you smoke per day, per week, and per month?".
- Only asked of participants who report that they are occasional/ daily smoking (if the participant reports quitting in the primary outcome they are excluded from this analysis)
- Percentage reduction in number of cigarettes smoked from baseline (dichotomised: at least 50% or < 50%)
- Reduction rate also to be calculated

v) Reducing cravings to smoke

- Frequency of cravings was assessed by one item^3: "How often do you get cravings to smoke tobacco?" with response options: a) hourly or more often, b) several times per day, c) at least once a day, d) less than daily, or e) never.

vi) Reducing withdrawal symptoms (24 hours, 30 days)

- 24 hours (measured at baseline and 3 months)

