Nicotine withdrawal symptoms over past 24hours was measured at baseline and 3-month follow-up using the Minnesota Nicotine Withdrawal Scale (MNWS), with symptoms [angry, irritable frustrated; anxious or nervous; depressed or sad; desire or craving to smoke; difficulty concentrating; increased appetite, hungry or weight gain; insomnia, sleep problems or awakening at night; restless or impatient] experienced in last 24 hours rated on an ordinal scale ranging from 0 (none), 1 (mild), 2 (moderate), to 3 (severe).

- Last 30 days (past week assessed at baseline; last 30 days at 3-month and 9-month follow-up)

A modified version of the MNWS was used to assess withdrawal symptoms over past 30 days. At baseline participants were asked "In the week before you came here, how often were you bothered by the following problems", and at 3-month and 9-month

follow-up timepoints “In the last 30 days, how often were you bothered by the following problems?” and asked to rate the list of withdrawal symptoms from 0 (not at all), 1 (several days), 2 (more than half the days), to 3 (nearly every day).

vii) Relapse episodes

- **Instance of relapse at 3-month follow-up** will be determined by:  
Answering ‘daily’ or ‘yes, at least once a week’ to question of “*do you currently smoke any tobacco products*”  
OR  
Answering ‘less often than once a week’ or ‘not at all’ to current smoking status **AND** answering ‘yes’ to question “*since you left service, have you smoked every day for a week or more?*”
- **Time to relapse at 3-month follow-up** is assessed by the question “How soon after discharge did you go back to smoking (your first smoke after discharge)?” with response options a) as soon as I could get a cigarette that day; b) later on the day I got out; c) on the day after I got out; d) 2-7 days after I got out; e) more than a week after I got out but less than 1 month; f) more than a month after I got out.
- **Instance of relapse at 9-month follow-up** is determined by:  
Answering ‘not at all’ to *current smoking status* **AND** responding ‘yes’ to question “*Since you quit smoking, have you smoked every day for a week or more (even just puffs)? (yes/no)*”  
OR  
Current (daily or occasional) smokers who report a quit attempt within past 6 months that lasted  $\geq 2$  days

vii) Abstinence from all nicotine/ tobacco products

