#### **4.5. Missing Data**

It is anticipated that there will be two main mechanisms that will enable missing data will be observed in the data sources for the primary and secondary outcome: 1) participant that have not completed the follow-up CATI surveys (at 3 or 9-months) and are considered lost to

follow-up; and 2) participants that were successfully reached at follow-up; however, the outcome is missing. It is expected the first scenario is most likely.

The main analysis will be conducted in the intention to treat population. The primary method of imputing missing data will follow the recommendations of the Russel Standard, and assume those with missing data to be not abstinent.

A sensitivity analysis will be conducted under the missing at random assumption and, if evidence of a treatment effect is shown then missing not at random (MNAR). The analysis will be conducted using multiple imputation by chained equations with predictive mean matching models (PMM). PMM models will use analysis variables (treatment, site, time and outcomes) plus variables known to be predictors of abstinence (???) and any variables found to be predictive of missingness. Chisq or t-tests on baseline psychometrics will be used to assess association with missingness on the primary outcome to include in the PMM models. The number of imputations will be the higher of the percentage missing or 25 and 20 iterations will be used. The stability of the results will be explored through increasing the number of imputations. Pattern mixture models will be used to assess the sensitivity of the missing at random assumption. A tipping point approach will be used by varying our assumptions regarding the outcome proportion for those with missing data in the treatment group until a positive treatment effect is nullified. This sensitivity analysis will enable a better understanding of the variability of the missing data and will be used to assess the impact of missing on the outcomes of the study.

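### Seven-month continuous abstinence is scored from month-9 recall alone, so a report of daily smoking at month 3, inside the window, is never checked against it

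*SAP*

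**What the plan says.** Section 4.1.1 defines the primary outcome as "Self-reported 7-month continuous abstinence (dichotomous: abstinent or not) at 9 months post randomization". It uses two items from the month-9 survey. The first is current smoking, which must be none at all. The second asks "How long ago did you last smoke every day" and offers banded answers; the bands for 7 to 9 months and for more than 9 months qualify. Those who are not smoking and give one of these two times "since they last smoked every day are considered to have reached 7-months continuous abstinence". The rule has no month-3 condition.

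Section 4.5 shows that there are two telephone surveys, since it describes participants who "have not completed the follow-up CATI surveys (at 3 or 9-months"). Section 4.1.2 shows what the month-3 survey records. "Instance of relapse at 3-month follow-up" is derived from current smoking status, where a daily answer counts as relapse, and from the item "since you left service, have you smoked every day for a week or more". Section 2.2.2 also lists "30-day point prevalence abstinence at months 3 and 9".

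For the verified outcome, section 4.1.2 says: "Self-reported 7-month continuous abstinence at 9-month survey will be verified using measures of CO in expired air". Sections 4.4 and 4.5 cover CO cut-offs, priors, baseline imbalance and missing data. Neither says which record prevails when the month-3 and month-9 answers disagree.

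**The concern.** An outcome called continuous abstinence over months 2 to 9 should not be credited to someone whom the trial recorded as smoking daily at month 3. The SAP can classify one participant both as relapsed at month 3 and as continuously abstinent over a period that includes month 3. Such a case fails the plan's own criterion, which concerns daily smoking. It is therefore a separate matter from whether occasional smoking should count.

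Few successes are expected, so a handful of wrongly credited ones could affect the main comparison if they fell unequally between arms. Participants know whether they were given a vaping device or NRT (section 3.2), so a difference in recall between arms is possible. Nothing in the SAP shows that it occurs.

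**Working it through.** **Window.** Start = 9 − 7 = month 2. Month 3 lies inside months 2 to 9, and 9 − 3 = 6 months before an on-time final survey.

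**How the rule treats someone smoking daily at month 3 who later quits**

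| True time since last daily smoking | Answer given at month 9 | Scored |
|---|---|---|
| up to 6 months (on-time survey) | 4 to 6 months or less, accurate | not abstinent |
| up to 6 months | 7 to 9 months, misremembered | success |
| 6 to 7 months (e.g. surveys 6.5 months apart) | no band fits; 4 to 6 months chosen | not abstinent |
| 6 to 7 months | no band fits; 7 to 9 months chosen | success |
| 7 months or more (final survey at about month 10 or later) | 7 to 9 months, accurate | success |

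In the last row there really are 7 months without daily smoking before the interview, so the month-3 record does not contradict the answer. The anchor adds some slack: section 4.1.1 counts 9 months from randomisation, section 3.1 from discharge.

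**Which month-3 item bears on this.** Current status does. The 30-day item asks about any smoking, even a puff, so it does not establish daily smoking. The item on daily smoking since leaving the service also covers the time before month 2, which the outcome permits.

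**Whether CO catches it.** No. It is measured at month 9 and says nothing about month 3, so the verified outcome and the stricter cut-offs in section 4.4 inherit the problem.

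**The plan's own figure (section 3.4).** Rates 3% and 9%, two-sided 5%, power 80%:

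- n = [1.96·√(2 × 0.06 × 0.94) + 0.842·√(0.03 × 0.97 + 0.09 × 0.91)]² / 0.06², which gives 245 per arm. With the continuity correction it is 278, as stated.
- For 40% attrition, 556 / 0.6 = 926.7, against the stated 926.

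The sample size reproduces and is not in dispute.

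**Expected successes.** If the rates apply to those followed up, 278 × 0.03 = 8.3 and 278 × 0.09 = 25.0. If they apply to all 463 randomised per arm (926 / 2), 463 × 0.03 = 13.9 and 463 × 0.09 = 41.7. Section 3.4 sizes the trial on 278 and then adds attrition, and section 4.5 scores missing as not abstinent. The first reading, about 8 versus 25, is therefore the natural one.

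**Effect of removing conflicts.** The SAP gives no share, so these are assumptions for illustration.

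*Equal share of successes removed in both arms.* At 30%, 3% and 9% become 2.1% and 6.3%.
- Risk difference: 6.0 to 4.2 points.
- Risk ratio: stays at 3.0.
- Odds ratio: (0.09/0.91)/(0.03/0.97) = 3.20 to (0.063/0.937)/(0.021/0.979) = 3.13.

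*Unequal removal, starting from 8 versus 25 out of 463 per arm* (odds ratio (25/438)/(8/455) = 3.25; difference 17/463 = 3.7 points).
- Five fewer in the VNP arm only: (20/443)/(8/455) = 2.57; difference 12/463 = 2.6 points.
- Two fewer in the NRT arm only: (25/438)/(6/457) = 4.35; difference 19/463 = 4.1 points.

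*Equal share of true non-abstainers wrongly credited.* If 1% are credited in each arm, 3% and 9% become 3.97% and 9.91%. The difference is almost unchanged at 5.94 points, but the odds ratio falls to (0.0991/0.9009)/(0.0397/0.9603) = 2.66. In terms of recorded successes this is unequal: 0.97/3.97 = 24% of the NRT arm's and 0.91/9.91 = 9% of the VNP arm's.

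**The case against.** The strongest reply is that the rule, answered correctly and on time, already fails the person described. The outcome is labelled as self-reported, every self-reported outcome is open to recall error, and leaving out a cross-check with an earlier survey is not a contradiction. This stands in large part. A reader might infer that the definition itself admits month-3 daily smokers. It does not: a false success needs a wrong band, or a gap that no band covers.

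Three further inferences also fail. Section 2.2.2 might suggest that the month-3 30-day item refutes a later claim of success, but any smoking is not daily smoking. One might assume that some sizeable fraction of successes is false, but the SAP supports no figure. One might conclude that the treatment effect is biased, but that depends on how the conflicts divide between arms, and equal shares of successes leave the odds ratio, which section 4.3.1 models, nearly unchanged.

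A check that can apply only to those seen at month 3 also has a risk of its own. If month-3 response differs by arm, the stricter standard is applied unequally.

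What remains is that section 4.1.1 gives a complete scoring rule, the contradicting record is collected, and nothing says how a conflict is settled.

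**Conclusion.** The gap is real but conditional. The primary outcome and its CO-verified version can count a participant as a success when the trial's own month-3 record rules it out. This happens only through misrecall, or through the uncovered 6-to-7-month interval. The frequency, direction and size of any bias are unknown. The point matters because few successes are expected (about 8 versus 25, assuming the planned rates apply to the 278 followed up per arm), so a few conflicts divided unequally would shift the estimate visibly. No stated figure is wrong and the outcome can be computed as written. This is a cheap improvement that I recommend; it is not something that must be corrected before the analysis can stand.

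**What to change.** In section 4.1.1, before arm-level data are seen, add the following:

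- A participant who reported current daily smoking at a month-3 interview held less than 7 months before the month-9 interview is scored not abstinent.
- If the month-3 survey is missing, the month-9 answers decide.
- The 30-day even-a-puff item is not used for this check.
- The same rule applies to the CO-verified outcome.

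Report by arm the month-3 completion and the number of conflicts, and give the result with and without the check. If the sponsor prefers to keep the month-9-only definition as primary, add the month-3-consistent scoring to section 4.4 as a prespecified sensitivity analysis.

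The cost is a few lines of SAP text and one data step, with no new data. Abstinence rates may fall slightly in both arms. Only participants seen at month 3 face the check, so unequal month-3 response could apply it unequally; reporting completion by arm and both scorings makes that visible. The rule does not close the gap between the response bands for participants without a month-3 interview.

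### The primary outcome is called 7-month continuous abstinence, but its rule looks back only for daily smoking, so weekly or occasional smokers who stopped before the month-9 interview count as successes

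*SAP*

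**What the plan says.** SAP section 4.1.1 names the primary outcome as "Self-reported 7-month continuous abstinence (dichotomous: abstinent or not) at 9 months post randomization". The null hypothesis in section 3.5 is that the two arms "will have an equal proportion of participants with self-reported 7-month continuous abstinence at 9-months follow-up", and the primary objective in section 2.2.1 uses the same term.

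The outcome is scored from two items at month 9:

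- "Do you currently smoke any tobacco products", which must be answered with the lowest of four categories (none);
- "How long ago did you last smoke every day", which must be answered with one of the two longest categories (7 to 9 months, or more than 9 months).

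Participants who satisfy both conditions on the time "since they last smoked every day are considered to have reached 7-months continuous abstinence". The section states no permitted number of lapses.

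Section 4.1.2 contains items that do ask about any smoking. One is "Have you smoked at all, even a puff, in the last 30 days", used for 30-day point prevalence, which section 2.2.2 schedules at months 3 and 9. The primary rule does not use it. The same section defines relapse at the 3-month survey partly by "Answering ‘daily’ or ‘yes, at least once a week’ to question of" current smoking.

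**The concern.** The first item describes the present. The second looks back, but only for smoking every day. Between the last day of daily smoking and the interview, weekly or occasional smoking is invisible to the rule. Seven months without daily smoking is a weaker condition than seven months of continuous abstinence, and the objective and hypothesis name the latter.

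This is the primary endpoint and the planned rates are low (3% and 9%), so a few misclassified participants per hundred change both the estimate and its meaning. If such smoking is more common in one arm than the other, the comparison itself is biased.

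**Working it through.** **1. What the rule admits.** The first item has 4 answers and the second has 6, giving 24 combinations. Two are scored abstinent: none with 7 to 9 months, and none with more than 9 months. Take a participant whose last daily smoking was before entering the unit, who smoked weekly in months 3 to 8 and who is not smoking at the interview. The truthful answers fall in one of those two cells, so the participant is a success. Someone still smoking weekly or less often at month 9 is not, because the first item excludes current smoking at any frequency. The affected group is therefore those who smoked non-daily inside the window and had stopped by the interview.

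**2. Comparison with the 3-month survey.** Seven months back from month 9 is month 2, so the 3-month survey lies inside the window. A participant smoking weekly at that survey is scored as relapsed under section 4.1.2. If that person never returned to daily smoking and later stopped, section 4.1.1 scores the same person as continuously abstinent at month 9. A participant smoking daily at month 3 should be caught by the look-back item.

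**3. Whether anything else closes the gap.**

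- CO verification (4.1.2) starts from the same self-report and is taken at the 9-month survey, so it cannot cover the earlier months. The stricter CO thresholds in 4.4 have the same limit.
- The 9-month relapse item for people not currently smoking again asks about daily smoking for a week or more.
- The Russell Standard appears in 4.4 and 4.5 only as the rule for missing data.
- No sensitivity analysis in 4.4 changes the self-report definition.

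**4. The plan's own sample size (section 3.4).** Inputs: 3% vs 9%, two-sided 5%, 80% power. The pooled normal-approximation formula gives 245 per group without a continuity correction and 278 with it, so 278 reproduces. Allowing for 40% attrition, 556 / 0.60 = 926.7, which matches the stated 926 apart from rounding.

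**5. Illustration of size.** Let f be the share of truly non-abstinent participants who pass the rule. The documents give no value for f, so every f below is an assumption. The observed rate is p + (1 − p) × f.

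| f in NRT | f in VNP | NRT rate | VNP rate | Difference (points) |
|---|---|---|---|---|
| 0 | 0 | 3.0% | 9.0% | 6.0 |
| 3% | 3% | 0.03 + 0.97 × 0.03 = 5.9% | 0.09 + 0.91 × 0.03 = 11.7% | 5.8 |
| 3% | 6% | 5.9% | 0.09 + 0.91 × 0.06 = 14.5% | 8.6 |
| 6% | 3% | 0.03 + 0.97 × 0.06 = 8.8% | 11.7% | 2.9 |

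Equal shares barely move the absolute difference but cut the risk ratio from 3.0 to 11.7 / 5.9 = 2.0. Unequal shares move the difference in either direction.

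**6. Power, equal 3% shares.** With the continuity correction and 278 per arm, power falls from 80% to 62%. The primary analysis, however, covers everyone randomised (4.1.5, 4.3.1), about 926 / 2 = 463 per arm. Reading 3% and 9% as rates in that population, power falls from 96% to 85%. These are frequentist figures on the basis of section 3.4; the planned analysis is Bayesian.

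**The case against.** **Is this a contradiction in the SAP?** A reader might infer one from the month-3 relapse rule. That goes too far. Relapse is a separate secondary outcome with its own definition, and its month-9 version for non-smokers also rests on daily smoking. The comparison shows that the primary rule is loose, not that two sections make incompatible statements.

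**Is the trial underpowered, or biased towards vaping?** Neither follows. The misclassification shares are assumed, power in the analysed population stays above 80% in the equal 3% case, and nothing in the SAP shows that intermittent smoking is commoner in the VNP arm. Nor is it certain that the planning rates used a stricter definition: section 3.4 calls the 3% verified continuous abstinence without defining it.

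**Is the 30-day outcome faulty too?** A reader might note that it combines two items, "Participants who report not having smoked in the last 30 days AND smoking 'less than 1' cigarette" or just a puff, and that the second item has no separate zero category. But zero is less than 1, and nothing says that abstainers skip the item. The documents do not support a fault there.

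**Can the collected items repair the primary outcome?** Only in part. The 30-day item covers the last month, and the 3-month survey gives current status at one time. Weekly smoking in months 4 to 7 would still pass. Requiring a clean 3-month survey only where it was completed would also test attenders more strictly than non-attenders, which could itself differ by arm. This objection stands and shapes the fix.

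**Is recent lapse already visible?** Yes, in part: 7-day and 30-day abstinence are planned secondary outcomes in the ITT population. That helps interpretation but does not change who counts as a primary success.

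**Conclusion.** The point holds. The primary rule excludes smoking of any frequency at the month-9 interview and daily smoking in the previous 7 months; it does not establish continuous abstinence. This follows from the wording of the two items and needs no assumption. The CO-verified secondary outcome inherits the problem.

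The size and direction of any bias cannot be obtained from the documents. With an assumed 3% of non-abstainers misclassified in both arms, 3% vs 9% would be observed as 5.9% vs 11.7%. With assumed shares of 3% and 6%, a true 6-point difference would appear as 8.6 or 2.9 points, depending on which arm has the larger share. The main harm is to the validity and labelling of the primary result; loss of power is secondary.

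**What to change.** Before unblinding:

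1. Add to the primary derivation a negative answer to the month-9 item on any smoking in the last 30 days. Apply the same condition to the CO-verified outcome.
2. Describe the outcome as what it then measures: no daily smoking for 7 months and no smoking in the last 30 days. State that non-daily smoking earlier in the window is not measured. Align the objective (2.2.1), hypothesis (3.5) and outcome (4.1.1) with this description.
3. Keep the present rule as a sensitivity analysis, labelled 7 months without daily smoking.
4. Add a stricter sensitivity analysis that also counts daily or weekly smoking at the 3-month survey as failure. Keep this condition out of the primary rule, because it depends on 3-month attendance.

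The change needs no new data. It costs a revised derivation, aligned wording in the objective and hypothesis (and in the protocol if it uses the same definition), and somewhat lower abstinence rates. It narrows the gap without closing it, which is why the description must change as well as the rule.
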